6.5.4 Right Heart Catheterization (RHC)

If during the LTE study the Investigator believes that a subject has normalized, or near normalized, their hemodynamics then a RHC, if clinically appropriate, is encouraged to confirm this. RHC parameters should be collected using the same methods that were used for the subject in AV-101-002. All PAH medications, chronic medications, and study drug should be taken as prescribed on the day of the RHC. The date of the RHC and the hemodynamic data should be entered into the eCRF.

6.5.4.1 Parameters measured during the RHC

6.5.4.1.1 Heart rate

Heart rate should be determined at the time of the cardiac output measure by thermodilution. Heart rate should be measured in duplicate until 2 consecutive values, measured during cardiac output assessment, do not differ by more than 10%. The last value should be recorded in the eCRF.

6.5.4.1.2 Cardiac Output by the Thermodilution method

Thermodilution is the preferred protocol recommended method for the measurement of CO. If the Fick method is used, then the VO₂ must be measured and not estimated. At least 3 determinations that are within 10% variability of one another must be measured. Measurements must be repeated until this reliability is met. The mean cardiac output will be defined as the average of these 3 measurements and used for the calculation of PVR. The mean value will be recorded on the eCRF.

If the mean cardiac output is auto-generated, Investigators must ensure that the measures used to calculate the mean are within the 10% variability and are available to be recorded on the eCRF. The last value will be recorded on the eCRF.

6.5.4.1.3 Systemic arterial pressure (systolic, diastolic, and mean):

Systemic arterial pressures should be taken just prior to entry of the catheter and should be measured in duplicate until 2 consecutive values do not differ by more than 10%. The last value should be recorded on the eCRF.

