6.5.4.1.8 Calculated parameters

- $PVR \text{ (dynes}\cdot\text{sec/cm}^5) = [(mPAP - PCWP) \div \text{mean cardiac output}] \times 80 \text{ or; } [(mPAP - LVEDP) \div \text{mean cardiac output}] \times 80$
- $CI = CO \div BSA$
- $SV = CO \div HR$
- Body Surface area (BSA; m²) = $0.007184 \times \text{weight}^{0.425} \times \text{height}^{0.725}$ where weight is in kg and height is in cm.

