8.5.3 Analysis of Tier 2 Effectiveness Endpoints

- **Change from LTE baseline in echocardiographic parameters at LTE Weeks 24, 48, 72 and 96 including (but not limited to) tricuspid annular peak systolic excursion (TAPSE), right ventricular myocardial strain, tricuspid annular systolic velocity (TA S'), and right ventricular fractional area change (RVFAC):** For each subject, the above echocardiographic parameters will be measured at LTE baseline and Weeks 24, 48, 72, and 96. The mean value and change from baseline at each visit will be summarized descriptively for each treatment group. The mean difference in change from baseline at each visit between subjects always on optimal dose (Group 1) and subjects always on placebo (Group 4) will be summarized and the 95%CI for the difference will be provided. Mean difference and the 95% CI between subjects always on optimal dose (Group 1) and subjects on placebo then active dose (Group 3) will be calculated, followed by taking the difference and the 95% CI between subjects always on optimal dose (Group 1) and subjects on non-optimal dose (Group 2). Mean change from baseline before and after optimal dose treatment during LTE will be presented.
- **Change from baseline in hemodynamics as assessed by RHC in LTE:** For those subjects who have RHC data, change from LTE baseline over time will be summarized for mPAP, PVR, cardiac output and mean right atrial pressure (mRAP), separately, by LTE treatment dose groups. Mean change from baseline before and after optimal dose treatment during the LTE will be presented.

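### Section 6.5.4.1.2 gives two conflicting instructions for recording cardiac output, so the recorded value can be a mean at some sites and a single last reading at others

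*Combined protocol and SAP*

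**What the plan says.** The first paragraph of protocol Section 6.5.4.1.2 sets a repeatability rule: "At least 3 determinations that are within 10% variability of one another must be measured". It then gives the definition and its use, "The mean cardiac output will be defined as the average of these 3 measurements and used for the calculation of PVR", and the recording instruction, "The mean value will be recorded on the eCRF".

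The second paragraph deals with equipment that produces the mean itself: "If the mean cardiac output is auto-generated, Investigators must ensure that the measures used to calculate the mean are within the 10% variability". It also requires that those component measures be available for entry on the eCRF. It closes with a different recording instruction: "The last value will be recorded on the eCRF".

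Section 6.5.4.1.8 divides by "mean cardiac output" in both versions of the PVR formula (wedge pressure and LVEDP). Cardiac index (CI) and stroke volume (SV) are written with CO, without saying whether it is the mean.

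Section 8.5.3 summarises change from LTE baseline in mPAP, PVR, cardiac output and mRAP for subjects who have RHC data.

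**The concern.** The two closing sentences give different answers to the question of which CO value goes on the eCRF, and the choice depends on the site's equipment. If sites follow the second sentence in the sense it has elsewhere in Section 6.5.4.1, two sites with identical readings will enter different CO values.

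CO is one of the four haemodynamic parameters listed for summary in Section 8.5.3, so the difference reaches a reported endpoint directly, whatever is done about PVR. It would mix two measurement definitions in one summary and add avoidable single-reading noise at some sites. RHC in the LTE is encouraged only in selected subjects (Section 6.5.4), so there may be few values over which to average that noise. The documents give no expected number.

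**Working it through.** The plan states no figure on this point, so there is nothing to reproduce. The check has two parts: what the disputed sentence means, and how large the discrepancy can be.

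**1. How Section 6.5.4.1 uses the wording**

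| Parameter | Section | Value to record |
|---|---|---|
| Heart rate | 6.5.4.1.1 | last reading ("The last value should be recorded in the eCRF") |
| Cardiac output, first paragraph | 6.5.4.1.2 | mean |
| Cardiac output, auto-generated mean | 6.5.4.1.2 | last value |
| Systemic arterial pressure | 6.5.4.1.3 | last reading |
| Pulmonary arterial pressure | 6.5.4.1.4 | last reading |
| Mean right atrial pressure | 6.5.4.1.5 | mean |
| PCWP or LVEDP | 6.5.4.1.6 | mean |
| Mixed venous saturation | 6.5.4.1.7 | last reading |

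Where the section wants a mean it says so. Elsewhere the last-value wording refers to the last of a repeated series. The natural reading of the CO sentence is therefore a single last reading, though the text does not say so outright.

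**2. Size of the discrepancy**

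Inputs: three readings (Section 6.5.4.1.2), and PVR proportional to 1/CO with the pressures held fixed (Section 6.5.4.1.8). Assumption: 10% variability means largest/smallest ≤ 1.10.

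Relative error in CO = last/mean − 1. Relative error in PVR, if the last reading replaces the mean, = mean/last − 1.

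The extremes occur when two readings sit at one limit and the last sits at the other:

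- Readings 1, 1, 1.1: mean = 3.1/3 = 1.0333. CO: 1.1/1.0333 = 1.0645, or +6.5%. PVR: 1.0333/1.1 = 0.939, or −6.1%.
- Readings 1.1, 1.1, 1: mean = 3.2/3 = 1.0667. CO: 1/1.0667 = 0.9375, or −6.3%. PVR: 1.0667/1 = 1.067, or +6.7%.

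A grid search over all triples meeting the rule confirmed these PVR limits.

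If the 10% is instead taken relative to the largest reading, the extreme triples are 0.9, 0.9, 1.0 and 1.0, 1.0, 0.9:

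- CO: 1.0/0.9333 − 1 = +7.1% and 0.9/0.9667 − 1 = −6.9%.
- PVR: −6.7% and +7.4%.

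Illustration, with an assumed mPAP − PCWP of 40 mmHg and assumed CO readings in L/min:

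- 4.0, 4.0, 4.4: mean 4.133 gives PVR = 40/4.133 × 80 = 774; last value gives 40/4.4 × 80 = 727.
- 4.4, 4.4, 4.0: mean 4.267 gives 750; last value gives 800.

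**3. Noise**

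With independent reading errors of SD σ, a single reading has measurement SD σ and the mean of three has σ/√3, a ratio of √3 = 1.73. The 10% acceptance rule limits how far the last reading can lie from the mean, so this is best read as an upper bound. It describes the measurement error of one CO value, not the SD of change from baseline.

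**The case against.** The strongest reply is that PVR is protected by the text. A reader might infer that the rule as written puts a single reading into PVR, CI and SV at every auto-generating site. The documents do not support that. Section 6.5.4.1.2 says that the mean is used for PVR, and Section 6.5.4.1.8 repeats it in both formulas. The disputed sentence concerns eCRF entry only. Derivation in the data capture system is stated only for mPAP (Section 6.5.4.1.4), so whether PVR is computed from the recorded CO is unknown. CI and SV are not among the parameters listed for summary in Section 8.5.3. This objection stands, and the PVR, CI and SV consequences must stay conditional.

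Other points have partial force:

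- The component readings must be available for entry, so the mean may be recoverable. But the only value the paragraph directs sites to record is the last one.
- The sentence could mean the last auto-generated mean that meets the 10% rule. That is possible, but usage in the neighbouring sections points the other way, and the protocol does not choose.
- Heart rate and pulmonary pressures are recorded as last readings by design, so some single-reading noise is already accepted. For CO, however, the protocol chose a mean.
- Section 6.5.4 asks for the same RHC methods as in the parent study. That protocol is not among the documents, so whether the recording rule differs between a subject's baseline and follow-up cannot be judged.

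**Conclusion.** The inconsistency is real and unresolved in the documents. At sites with an auto-generated mean, the recorded CO can be a single reading while other sites record the mean of three, and recorded CO is itself a summarised parameter. PVR is exposed only if it is derived from the recorded value, contrary to the protocol's own definition.

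The 6% to 7% differences are worst cases for individual measurements and depend on how the 10% rule is read; they are not expected biases. The √3 ratio requires independent reading errors. Practical importance is low: RHC is optional, the RHC item in Section 8.5.3 is a descriptive Tier 2 summary with no test planned for it, and neither the main safety analyses nor the number of subjects is touched. It is a minor correction, worth making because it costs almost nothing.

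**What to change.** Replace the last sentence of the second paragraph of Section 6.5.4.1.2 with: *The auto-generated mean, and the three qualifying readings it is based on, will be recorded on the eCRF.* Add that CO summaries and PVR, and CI and SV if derived, use that mean at all sites. Stating what the 10% is measured against would also remove the ambiguity in the acceptance rule.

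The cost is a sentence or two in the protocol and, if they are not already there, eCRF fields for the three readings. No extra procedure or measurement is needed, since the section already requires the readings to be taken and to be available. Where RHC data have already been entered, sites with auto-generated means should be asked which value was recorded and, where the component readings exist, the mean should be restored.

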6.5.4.1.4 PAP (systolic, diastolic, and mean)

Pulmonary arterial pressures should be measured at end expiration and should be measured in duplicate or until 2 consecutive values do not differ by more than 10%. The last value will be recorded on the eCRF.

Mean PAP (mPAP) is derived in the electronic data capture (EDC) system per the following equation:

$$\text{mPAP} = ([\text{diastolic PAP} \times 2] + \text{systolic PAP}) \div 3$$

6.5.4.1.5 Mean right atrial pressure (mRAP)

Mean RAP should be measured in duplicate and the mean value calculated and recorded on the eCRF.

6.5.4.1.6 Pulmonary Capillary Wedge Pressure (PCWP) or Left Ventricular End Diastolic Pressure (LVEDP)

The PCWP or LVEDP should be recorded as the mean of 3 measurements at end-expiration. It is strongly preferred that the same assessment (PCWP or LVEDP) be performed for both RHC

assessments. In situations where this is not possible, the Investigator should provide an explanation in the eCRF.

The following additional recommendations from the 5th World Symposium working group on definitions and diagnosis of pulmonary hypertension ([Hoeper 2013b](#)) should be considered:

- Zero the pressure transducer at the midthoracic line in a supine patient halfway between the anterior sternum and the bed surface. This represents the level of the left atrium.
- The balloon should be inflated in the right atrium from where the catheter should be advanced until it reaches the PCWP position. Repeated deflations and inflations of the catheter should be avoided because this has been associated with ruptures of pulmonary arteries (PAs).

6.5.4.1.7 Mixed venous oxygen saturation (SVO₂):

Blood gas from a pulmonary artery mixed venous blood sample should be measured in duplicate or until 2 consecutive values do not differ by more than 3%. The last value should be recorded on the eCRF.

6.5.4.1.8 Calculated parameters

- $PVR \text{ (dynes}\cdot\text{sec/cm}^5) = [(mPAP - PCWP) \div \text{mean cardiac output}] \times 80 \text{ or; } [(mPAP - LVEDP) \div \text{mean cardiac output}] \times 80$
- $CI = CO \div BSA$
- $SV = CO \div HR$
- Body Surface area (BSA; m²) = $0.007184 \times \text{weight}^{0.425} \times \text{height}^{0.725}$ where weight is in kg and height is in cm.

6.5.5 Resting Transthoracic Echocardiogram (ECHO)

Instructions for the collection and transmittal of ECHOs to the core laboratory will be provided in a separate study-specific imaging manual. Images will be digitized and stored to an optical disk for subsequent analysis.

A core imaging laboratory will collect all echocardiographic data and provide centralized blinded adjudication safety and efficacy assessments, including those listed as secondary endpoints of right ventricular function. The following parameters will be assessed: tricuspid annular peak systolic excursion (TAPSE), right ventricular myocardial strain, tricuspid annular systolic velocity (TA S'), right ventricular fractional area change (RVFAC), RV/PA coupling (TAPSE/PASP) and tricuspid regurgitant jet velocity (TRJV). The study-specific imaging manual will contain a complete list of the required parameters.

The Investigator will review the ECHOs for any clinically significant abnormalities to ensure subject safety. Abnormal changes in ECHO findings from baseline that are considered clinically

significant by the Investigator should be reported as AEs and recorded in the AE eCRF page if the finding meets the definition of an AE.

A core imaging laboratory will conduct a central analysis of the echocardiographic data.

6.5.6 Clinical Laboratory Assessments

Blood samples will be collected and sent for testing at the Central Laboratory. Refer to [Table 2](#) for the required clinical laboratory tests and to the Schedule of Assessments for the time points. Specific instructions for processing, labeling, and shipping samples will be provided in a Central Laboratory Manual. Urine pregnancy test kits are provided for women who require testing. Urine pregnancy tests are performed locally during clinic visits and home testing.

- All samples should be clearly identified.
- Additional tests may be performed at any time during the study, as determined necessary by the Investigator or as required by local regulations.
- The tests will be performed by the central laboratory unless otherwise noted.
- The Investigator must review each laboratory report, document their review, and record any clinically relevant changes occurring during the study in the source documents and in the AE section of the eCRF. The laboratory reports must be filed with the source documents.
- Non-fasting blood samples are acceptable for this study.
- Repeat laboratory testing may be required during the study for various reasons, e.g., loss of sample en-route to the Central Laboratory. Any testing which is required to be repeated should be reevaluated as soon as possible after the designated visit.

6.5.6.1 Clinical Safety and Screening Evaluations

Table 2 Laboratory Assessment Parameters

Laboratory Assessments	Parameters		
Hematology	Hematocrit Hemoglobin Mean corpuscular hemoglobin Mean corpuscular hemoglobin concentration Mean corpuscular volume Platelet count	RBC Indices: MCV MCH %Reticulocytes	WBC Count with Differential: Neutrophils Lymphocytes Monocytes Eosinophils Basophils
Clinical Chemistry	Albumin Alkaline phosphatase Alanine aminotransferase Aspartate aminotransferase Total bilirubin Bilirubin-direct (only if total bilirubin is outside the normal range)	Calcium Serum creatinine (eGFR will be calculated from serum creatinine using the CKD-EPI equation)	Glucose Potassium Sodium Total protein Uric acid
Other Tests	The FSH test may be performed at Screening, per Investigator’s discretion to confirm post-menopausal state. For women of childbearing potential, urine pregnancy testing is performed at each study visit, and home pregnancy testing is required every 4 weeks, from randomization, between study visits.		

6.6 Other Assessments

6.6.1 NT-proBNP

NT-proBNP is a biological marker which is known to be released in response to changes in pressure inside the heart. Storage and analyses of samples will be handled according to the study Lab Manual.

6.6.2 Study Questionnaire (emPHasis-10)

In the LTE study the quality-of-life instrument used will be the emPHasis-10 questionnaire. The emPHasis-10 is a short 10 question questionnaire used to assess the health-related quality of life (HRQoL) in patients with pulmonary hypertension (PH). Each question uses a 6-point semantic scale (0 – 5) for a maximum score of 50.

Please refer to [Appendix 2](#) for the sample study questionnaire.

6.6.3 6-Minute Walk Test and Borg Dyspnea Scale

6.6.3.1 6-Minute Walk Test (6MWT)

The 6MWT will be conducted according to the European Respiratory Society/American Thoracic Society technical standard for field walking tests [in accordance with local standard operating procedures], and following guidelines established by [Holland et. Al. \(2014\)](#). Please see [Appendix 3](#) for guidance based on [Holland et al.](#)

6.6.3.2 Borg Dyspnea Scale

Subject perception of breathlessness after exertion will be reported using the Borg CR Scale® (CR10). The BDI score will be assessed immediately following completion of the 6MWT. Please refer to [Appendix 4](#) for guidelines on conducting the BDI.

6.6.4 WHO Functional Class

WHO FC will be assessed at all study visits.

Class Description

- | | |
|------------|--|
| Class I: | Pulmonary hypertension but without resulting limitation of physical activity. Ordinary physical activity does not cause undue dyspnea or fatigue, chest pain or near syncope. |
| Class II: | Pulmonary hypertension resulting in slight limitation of physical activity. Subject is comfortable at rest. Ordinary physical activity causes undue dyspnea or fatigue, chest pain or near syncope. |
| Class III: | Pulmonary hypertension resulting in marked limitation of physical activity. Subject is comfortable at rest. Less than ordinary physical activity causes undue dyspnea or fatigue, chest pain or near syncope. |
| Class IV: | Pulmonary hypertension with inability to carry out physical activity without symptoms. Subject manifests signs of right heart failure. Dyspnea and/or fatigue may even be present at rest. Discomfort is increased by any physical activity. |

The Investigator will complete the WHO Functional Class assessment. Every effort should be made to have the same Investigator or medically qualified designee assess the subject at each study visit.

6.6.5 Clinical Worsening

Clinical worsening events will be defined as:

- Death (all causes)

- Hospitalization for worsening PAH
- Initiation of parenteral prostanoids
- $\geq 15\%$ decline from baseline in 6MWD accompanied with continued or worsening WHO FC III or IV symptoms. The decline in 6MWD must be confirmed with a repeat test on a different day within 2 weeks. (Baseline is defined by the randomization visit in Study AV-101-002 for those on AV-101 and the Week 24 visit for those on placebo in Study AV-101-002).

